#### Secondary analysis of other populations that are defined above.

These include “ever treated”, “combination treatment” and “combination threshold treatment” as described above.

## 8.5 Adverse Event tabulation and classification

FIGURE 8: AE classification by population

AEs will be classified in each of these categories:

| Population name | ITT population                                            | Ever-treated population                                    | Combination ever-treated population                                               | Combination Threshold population                                                 |
|------------------------|-----------------------------------------------------------|------------------------------------------------------------|-----------------------------------------------------------------------------------|----------------------------------------------------------------------------------|
| AE category     | After enrollment but before any study drug administration | After administration of at least one dose of pembrolizumab | Among those with at least one dose of pembrolizumab and at least one dose of IL-2 | Among those with at least 6 doses of pembrolizumab and at least 10 doses of IL-2 |
| Unrelated              |                                                           |                                                            |                                                                                   |                                                                                  |
| Possibly related       |                                                           |                                                            |                                                                                   |                                                                                  |
| Probably related       |                                                           |                                                            |                                                                                   |                                                                                  |
| Definitely related     |                                                           |                                                            |                                                                                   |                                                                                  |

AEs *possibly, probably or definitely* related to the study treatment (shaded area) will be summarized by system organ class and preferred term.

Listings and summary tables will be provided.

Separate data listings and summaries will be presented for all serious adverse events (SAEs) and deaths.

1. Safety monitoring: Sequential boundaries will be used to monitor dose-limiting toxicity rate. The method is developed by Ivanova, Qaqish, and Schell (Biometrics, 2005) Briefly, the accrual of new patients to the trial will be suspended to accommodate re-evaluation of safety issues if the number of patients with dose-limiting toxicities is equal to or exceeds  $b_n$  out of  $n$  patients who are part of the *combination treatment population* (see table). This is a Pocock-type stopping boundary that yields the probability of crossing the boundary at most 0.05 when the rate of dose-limiting toxicity is equal to the acceptable rate 0.15.

Patients who have already enrolled, but not yet started on treatment with any pembrolizumab, at a point in time at which the accrual was suspended may be treated at the discretion of the investigator based on the safety evaluation.

*FIGURE 9: Table of Pocock boundary evaluation*

| Table for number of patients $k$ and Pocock boundary $b_k$ |   |   |   |   |   |   |   |   |   |    |    |    |    |    |    |    |    |    |    |    |    |    |    |    |  |  |
|------------------------------------------------------------|---|---|---|---|---|---|---|---|---|----|----|----|----|----|----|----|----|----|----|----|----|----|----|----|--|--|
| Number of Patients, $k$                                    | 1 | 2 | 3 | 4 | 5 | 6 | 7 | 8 | 9 | 10 | 11 | 12 | 13 | 14 | 15 | 16 | 17 | 18 | 19 | 20 | 21 | 22 | 23 | 24 |  |  |
| Boundary, $b_n$                                            | - | - | 3 | 3 | 4 | 4 | 4 | 5 | 5 | 5  | 5  | 6  | 6  | 6  | 6  | 7  | 7  | 7  | 7  | 8  | 8  | 8  | 8  | 8  |  |  |
|                                                            |   |   |   |   |   |   |   |   |   |    |    |    |    |    |    |    |    |    |    |    |    |    |    |    |  |  |

If the number of patients  $k$  who have DLT events that are *possibly, probably or definitely* related equals or exceeds the boundary  $b_k$ , the accrual to the trial will be suspended pending reevaluating toxicity by study PI and the Protocol Monitor Committee (PMC). This may include recommendations on patients who have already started on treatment.

The DLT events for this safety purpose will *exclude* events that are judged by the PI to be typical for IL-2 treatment, referencing the experience as described in the package insert for Proleukin™ and have resolved by the point in time that the next dose of pembrolizumab is due. The DLT events to be counted here will include at least those defined as in section 7.3.4 as these:

- AEs leading to permanent dosing discontinuation of either pembrolizumab or HD IL-2
- AEs  $\geq$  Severity Grade 3 occurring after the HD IL-2 administration dates
- Unexpected (according to medical judgment) AEs
- Additionally, other events that the PI may designate.

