## **2.1 TRIAL DESIGN**

### **2.2 Trial Design**

Overall schedule plan: The treatment is organized into blocks of 9 weeks, with pembrolizumab treatment planned for weeks 1, 4 and 7. On the second and third blocks, interleukin-2 is added, for 5 doses at a time, one dose every 8 hours, on a weekly schedule on the two weeks after the week 1 and the week 4 pembrolizumab doses. This works out to a plan of 20 doses per 9 week block. The fourth block is again pembrolizumab monotherapy, as was the first. If delays occur prior to the 2nd or 3rd block, up to one additional 3 week (one dose) pembrolizumab dose may be added, to keep the overall pattern, within the second and third blocks. If a complete response is identified (including after block 1), then pembrolizumab can be continued as specified to the end of block 4, or stopped sooner after at least 2 interval scans showing complete response, at the discretion of the treating physician or the study PI. The protocol specified treatment finishes after the end of the 4th block. This will typically be 36 weeks after start, but extra 3-week cycles of pembrolizumab are allowed, if needed to maintain the overall schedule, so duration of treatment may turn out to be a month or two longer.

There is no dose escalation portion: The dose and schedule of IL-2 is fixed, 600,000 IU/kg/dose, with a cap of 66 mIU/dose. Doses may be omitted for safety. The dose of pembrolizumab is fixed, flat dose 200 mg/dose.

Safety monitoring: Sequential boundaries will be used to monitor dose-limiting toxicity rate. There is a detailed plan in section 8.5

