### 3.1 OBJECTIVES & HYPOTHESES

#### 3.2 Primary Objective & Hypothesis

(1) **Objective-Efficacy portion:** Estimate the frequencies of disease response so as to be a basis to commit to more development of this schedule. Note that this is framed broadly, with the understanding that the decision to commit to further development of the schedule includes a variety of feasibility endpoints.

The ORR will be defined as the CR + PR patients, with confirmation of the response status (numerator), among those ever treated (denominator). **Hypothesis:** For the efficacy portion  $H_0$ : ORR is  $<20\%$  and  $H_A$ : ORR is  $>45\%$ . Thus, a 45% ORR (CR + PR) would be considered of definite interest for further development, contingent on the feasibility assessment as well, as part of the decision. With a Simon 2-stage design, 24 evaluable patients are needed.

**Objective –Safety portion:** The co-primary endpoint of adverse event and serious adverse event tabulation comprises a critical portion of the ultimate assessment of feasibility for moving forward with additional and directly comparative trials using this regimen. There are known frequencies of these (referencing the respective monotherapy prescribing information documents) for which this tabulation can be compared. The relatively small sample size of this series versus those series typically would prevent specific hypothesis testing.

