Checkpoints and cytokines, together: Every lymphocyte that is an effector of checkpoint inhibition response has IL-2 receptor on it (NK cells, T cells, B-cells all have IL-2 receptors). Conversely, every IL-2 activated lymphocyte, whether bearing low & intermediate affinity receptor (CD25 [IL2Ra] or CD 122 & 132 [IL2R $\beta$  & IL2R $\gamma$ ]) or high affinity receptor (CD25, CD122, CD132) has potential to have been modulated by PD-1 pathway, or to be later affected either directly through its own PD-1 receptors, or indirectly through the changed behavior of other lymphocytes bearing PD-1 receptor. As described by in our recent AACR poster (Choueiri *et al* 2014) PD-1 inhibition in kidney cancer patients induces two changes that are encouraging for synergy – more intratumoral lymphocytes, and more IL-2 receptor ( $\beta$ chain).

The core common feature of these immune therapies is that the lymphocytes bear receptors of both of these drugs and the intratumoral resistance mechanisms remain to be completely defined. One common feature, for example, may be that tumors with no discernable penetration by leukocytes are resistant. Another may be that patients with a high burden of tolerance promoting myeloid derived suppressor cells will not reach a response. How will NK and T cells respond to IL-2 in the context of PD-1 inhibition? That is the central biological question. That biological question is fundamental to the key clinical questions: Will more tumors regress? Will immunologic side effects be amplified in the short term? Will immunologic side effects be amplified in the long term? Both drugs have limitations—IL-2 with short term toxicity, pembrolizumab with unestablished durability of responses, potential for late autoimmune toxicity, and both with limited overall response frequency and incomplete algorithms for patient selection. However, this study will work towards finding a regimen that is feasible, and ultimately raising rates of durable, unmaintained remissions the central goal of oncolytic therapeutics.

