| Duration                  | Record the start and stop dates of the adverse event. If less than 1 day, indicate the appropriate length of time and units                                                                                                                                                                                                                                                                                                                                                                                                                                                                                                                                                                                                                                                                                                                                                                                                                                                                                  |                                                                                                                                                                                                                                                          |

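### Figure 8 assigns adverse events to the combination columns by patient, not by onset, so the planned co-primary safety table does not separate events before IL-2 from events after it

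*Combined protocol and SAP*

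**What the plan says.** Section 3.2 gives the AE table its status: "The co-primary endpoint of adverse event and serious adverse event tabulation comprises a critical portion of the ultimate assessment of feasibility". It names the two monotherapy labels as the comparison and says the sample is too small for formal testing.

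Figure 8 in section 8.5 has four columns:
- ITT: "After enrollment but before any study drug administration".
- Ever-treated: "After administration of at least one dose of pembrolizumab".
- Combination: "Among those with at least one dose of pembrolizumab and at least one dose of IL-2".
- Combination threshold: "Among those with at least 6 doses of pembrolizumab and at least 10 doses of IL-2".

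The rows grade relatedness to study treatment as a whole, from unrelated to definitely related. Figure 7 in section 8.3 defines the combination and threshold populations by doses received and likewise has no onset condition.

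On timing, section 2.2 adds IL-2 only in blocks 2 and 3: "The fourth block is again pembrolizumab monotherapy, as was the first". Section 5.2.2 (Timing of Dose Administration) sets the first IL-2 admission 2 to 9 days, usually 7, after the first block 2 pembrolizumab dose. Section 7.3 starts AE recording at Cycle 1 Day 1, and Table 6b in section 7.3.4 asks sites to "Record the start and stop dates of the adverse event". Section 4.5 lists among the key clinical questions: "Will immunologic side effects be amplified in the short term", with a matching question for the long term.

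**The concern.** Figure 8 mixes two kinds of definition. Its first two columns are time windows and its last two are sets of patients. A patient who has an immune-related event on pembrolizumab alone in block 1, and then one IL-2 dose in block 2, contributes that event to the combination column. The ever-treated column has no end at first IL-2, so it holds the same patients' later events as well.

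The schedule provides a pembrolizumab-only period in the same patients before IL-2 starts. It is the only reference inside this single-arm trial for what IL-2 adds, and the planned summary table does not use it. A reader of the co-primary output would see events under a combination label without knowing how many came before the combination began.

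**Working it through.** **Stated figure in the same section.** The only operating figure in section 8.5 is the toxicity boundary's crossing probability, stated as at most 0.05 at a true rate of 0.15. An exact binomial recursion over the printed boundary for 1 to 24 patients gives 0.0468, which agrees. The present point does not depend on it.

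**What each column counts** for a patient who goes on to receive IL-2:

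| Figure 8 column | Defined by | AE before first IL-2 | AE after first IL-2 |
|---|---|---|---|
| ITT | time | only before any study drug | no |
| Ever-treated | time, no upper limit | yes | yes |
| Combination | patient | yes | yes |
| Combination threshold | patient | yes, if doses reached | yes, if doses reached |

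No column stops at first IL-2 and none starts there. The ever-treated and combination columns differ only by patients who never had IL-2. With 26 subjects in all (section 1.0) and 24 in the combination population (section 8.4), that is 2 patients. Section 8.4 can also be read as allowing 26 with IL-2, which leaves that gap undefined.

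**Length of the pre-IL-2 window.**
- Block 1: 9 / (4 × 9) = 9/36 = 25% of planned treatment time.
- To first IL-2 on nominal intervals: 63 + 2 = 65 to 63 + 9 = 72 days, usually 70. Of 36 × 7 = 252 days this is 65/252 = 26% to 72/252 = 29%.
- Of the AE window including the 30 days after treatment (282 days): 23% to 26%.
- The extra cycle allowed before block 2 would lengthen it.

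**What the pooled column hides (illustration).** The documents give no AE rates, so these are assumptions: constant weekly hazard h before IL-2 and m × h afterwards, first IL-2 at t = 10 weeks, and T = 36 + 30/7 = 40.29 weeks. Risk before IL-2 is 1 − exp(−10h), risk after is 1 − exp(−m × 30.29 × h), and the combination column shows 1 − exp(−h(10 + 30.29m)).

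Fix the combination column at 40%, so h = −ln(0.6) / (10 + 30.29m):

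| m | Risk before IL-2 | Risk after IL-2 | Combination column |
|---|---|---|---|
| 1 (no amplification) | 11.9% | 31.9% | 40% |
| 2 | 7.0% | 35.5% | 40% |
| 3 | 4.9% | 36.9% | 40% |

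The same column value fits all three. The expected share of its events arising before IL-2 is 10/40.29 = 25% if IL-2 changes nothing and 10/70.57 = 14% if it doubles the rate.

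Range for m = 1: if 5%, 10%, 20% or 30% of patients have the event in 9 weeks, the combination column shows 20.5%, 37.6%, 63.2% or 79.7%. The period from first IL-2 shows 15.9%, 29.9%, 52.8% or 69.9%.

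**How precise a split table would be.** Over the same range the pre-IL-2 risk is 5.5% to 32.7%, or 1.3 to 7.8 of 24 patients. Suppose instead a 20% risk over 36 weeks on pembrolizumab alone. Then h = −ln(0.8)/36, the 9-week risk is 1 − exp(−9h) = 5.4%, or 1.3 of 24 patients, and the chance of no event at all is exp(−24 × 9h) = 26%. As an example, 1 event in 9 weeks against 6 in 18 weeks gives an exact 95% interval for the rate ratio of about 0.4 to 138. This comes from the Clopper–Pearson limits for 6/7 (0.421 and 0.9964), each turned into odds and multiplied by 9/18.

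**The case against.** The strongest reply is that Figure 8 is a table by population and does that job. The ever-treated column is the safety evaluation population of Figure 7, so it should hold all on-treatment events. A reader might take it for a pembrolizumab-only column that has been contaminated; the documents never call it that. Section 3.2 compares the tabulation with the monotherapy labels, and whole-treatment totals per patient suit that purpose. The amplification question stands in the rationale, not among the objectives. All of this is right, and it is why the totals should stay. It does not explain why the combination columns should include time before the combination.

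A reader might also infer that the trial cannot show whether IL-2 amplifies toxicity. The documents do not support that. Start and stop dates are recorded, listings are planned, and section 5.7.1 attributes each AE to pembrolizumab, IL-2, both or neither. Table 6a begins at first IL-2, and one dose-limiting toxicity item is limited to events after IL-2. The gap is in the summary table, whose rows do not carry the section 5.7.1 attribution. The time wording of the first two columns suggests that successive windows may have been intended, but the last two do not say so.

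The opposite overreach is that an onset split would recover the true effect of IL-2. It would not, for four reasons:
- The counts are small, as shown above.
- Period is confounded with time on pembrolizumab.
- Pre-IL-2 events within the combination population are selected. An ongoing Grade 2 or worse pembrolizumab event counts against an IL-2 dose on the section 5.2.4 checklist, and patients who become unfit for IL-2 are replaced (Subject Replacement Strategy). Severe early toxicity tends to drop out of that group, which would make amplification look larger. For the same reason, 25% is a share of time and may overstate the share of severe events.
- Section 7.3 limits recording to pembrolizumab-related AEs and leaves expected IL-2 AEs off the case report form, while Table 6a calls for several kinds of AE from first IL-2. Ascertainment may differ between periods.

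**Conclusion.** The point holds for the planned table. As written, AEs from the pembrolizumab-only period (9 weeks plus 2 to 9 days) in anyone who later receives one IL-2 dose are tabulated as combination AEs, and the ever-treated column pools both periods too. No section plans a split at first IL-2. About a quarter of planned treatment time is affected; the share of events is unknown and was 14% to 25% under the constant-hazard assumptions above.

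This should be corrected because the tabulation is co-primary and the change is cheap. It alters no error rate, sample size or stopping rule. The conclusion rests on the plain wording of Figures 7 and 8 and on nominal dosing intervals; the illustrative rates are assumptions and do not carry it.

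**What to change.** In Figure 8, split AEs by date of onset or worsening:
- (a) first pembrolizumab dose to just before first IL-2 dose, in all ever-treated patients;
- (b) first IL-2 dose to the end of block 3;
- (c) block 4 and follow-up.

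Give patients at risk and patient-weeks for each period, carry the four-way attribution of section 5.7.1 into the rows, and keep the patient-level totals for the label comparison in section 3.2.

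State in section 8.5 that the contrast is descriptive and imprecise, and that period is confounded with time on pembrolizumab. Name (a) in all ever-treated patients as the main reference, because early events within the combination population are selected. Reconcile the recording limits in section 7.3 with Table 6a so that ascertainment is comparable across periods.

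The split itself costs a wording change and one re-cut of the tables, using dates already collected. Reconciling the recording rules is the larger task and may affect what sites enter after IL-2 starts.

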### 7.3.4 Evaluating Adverse Events

An investigator who is a qualified physician will evaluate all adverse events according to the NCI Common Terminology for Adverse Events (CTCAE), version 4.0. Any adverse event which changes CTCAE grade over the course of a given episode will have each change of grade recorded on the adverse event case report forms/worksheets.

All adverse events regardless of CTCAE grade must also be evaluated for seriousness.

For the purpose of this study, IL-2 AEs/SAEs will be recorded and reported as follows:

*Table 6a: AE evaluation timeline*

| Record and Report:                                                                                                                                                                                                                                                                                                                                            | Begin                 | End                                                |
|----------------------------------------------------------------------------------------------------------------------------------------------------------------------------------------------------------------------------------------------------------------------------------------------------------------------------------------------------------------------|------------------------------|-----------------------------------------------------------|
| 

 AEs leading to permanent dosing discontinuation of either pembrolizumab or HD IL-2

 AEs <math>\geq</math> Severity Grade 3 occurring after the HD IL-2 administration dates

 Unexpected (according to medical judgment) AEs

 | Following first dose of IL-2 | Patient has terminated, withdrawn, or completed the study |

Pre-existing conditions (i.e., noted before study drug administration) should not be reported as AEs unless they worsen (i.e., become more severe or more frequent) following administration of either study drug.

Metastatic clear-cell Renal Cell Carcinoma disease progression is study endpoint information and should not be reported as an adverse event.

Events **not** considered to be serious adverse events are hospitalizations for:

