### 8.3 Statistical Analysis

#### *Study population definitions*

The primary endpoint, ORR, will be estimated, along with a with one-sided 95% confidence interval, counting evaluable patients (the “combination treatment population”) getting at least one per-protocol dose of IL-2, using binomial distribution theory.

The response assessment and safety assessment populations are defined for the analyses as follows:

*FIGURE 7: Population definitions*

| name                                                 | description                                                                   |
|-------------------------------------------------------------|--------------------------------------------------------------------------------------|
| Intent to treat (ITT) population
(ITT efficacy analysis) | Eligible and registered                                                              |
| Ever-treated population
(Safety evaluation population)   | At least one dose of pembrolizumab                                                   |
| Combination treatment population                            | At least one dose of pembrolizumab (start of block B1) and at least one dose of IL-2 |

|                                  |                                                                                          |
|----------------------------------|------------------------------------------------------------------------------------------|
|                                  | (usually indicating a start of block B2, and usually at least 4 doses of pembrolizumab). |
| Combination threshold population | At least 6 doses of pembrolizumab and at least 10 doses of IL-2 (In any block).          |

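### The section 8.5 DLT boundary counts patients in n from their first IL-2 dose, before their DLT outcome is known, so read literally it can flag an early excess late or miss it

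*Combined protocol and SAP*

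**What the plan says.** Section 8.5 (Safety monitoring) sets the rule: "accrual of new patients to the trial will be suspended to accommodate re-evaluation of safety issues if the number of patients with dose-limiting toxicities" is at least b_n, where n is the number of patients in the combination treatment population. Figure 7 in section 8.3 defines that population as "At least one dose of pembrolizumab (start of block B1) and at least one dose of IL-2". A patient therefore enters n on the first day of IL-2.

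The boundary is described as a "Pocock-type stopping boundary that yields the probability of crossing the boundary at most 0.05", with 0.15 as the acceptable DLT rate. Figure 9 prints b_k for k = 1 to 24.

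On the events themselves, section 8.5 says: "The DLT events to be counted here will include at least those defined as in section 7.3.4 as these". The list that follows covers permanent discontinuation of either drug, grade 3 or worse events after the IL-2 dates, unexpected events, and others that the PI may designate. In section 7.3.4, Table 6a records the first three types from "Following first dose of IL-2" to "Patient has terminated, withdrawn, or completed the study". Section 7.3 gives a different end for adverse event recording, 30 days after treatment stops. Section 5.2.1.2 expects that pembrolizumab-related events may appear months after the last dose.

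The plan gives no DLT observation window, no minimum follow-up for counting in n, and no statement of when the boundary is checked or in what order patients are taken.

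**The concern.** A boundary of this kind has its stated properties when each patient's DLT status is known at the time that patient is counted. Here the denominator grows on dosing day, while the numerator can grow for months. Patients with no time at risk therefore count, in effect, as free of DLT and lift the threshold.

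For example, three DLTs among the first four patients meet b_4 = 3. If the third DLT appears after patient 5 has had one IL-2 dose, the count of 3 is set against b_5 = 4 and nothing is flagged. If it appears when seven patients have started, it is set against b_7 = 4, with the same result.

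Section 4.4.4.1 describes the trial as the first human experience of the two drugs on this schedule, and Figure 9 is its only numerical safety boundary. The action is to suspend accrual, so a late flag loses most of its use. Delayed DLTs are plausible: IL-2 is spread over two 9-week blocks, and section 8.5 removes typical IL-2 events that resolve before the next pembrolizumab dose.

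**Working it through.** **Inputs from the documents**
- Boundary b_1 to b_24 (Figure 9): –, –, 3, 3, 4, 4, 4, 5, 5, 5, 5, 6, 6, 6, 6, 7, 7, 7, 7, 8, 8, 8, 8, 8.
- Acceptable DLT rate 0.15; crossing probability at most 0.05 (section 8.5).
- 26 patients, enrolled from 4/2017 to 3/2019 (section 1.0): 24/26 = 0.92 months between patients.
- Blocks B2 to B4: 3 × 9 = 27 weeks, roughly first IL-2 to end of treatment.

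**Assumptions, not in the documents**
- True DLT rates of 0.30 and 0.40.
- DLT onset uniform over W weeks from first IL-2, with W from 4 to 27.
- Patients start IL-2 at random (Poisson) at the average rate above.

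**Step 1. Reproduce the plan's figure.** Let P_k(s) be the probability of s DLTs among the first k patients with no crossing so far. With outcomes known at once, P_k(s) = (1 − p) P_{k−1}(s) + p P_{k−1}(s − 1) for s < b_k. Because b_k never falls, the probability of first crossing at k is p P_{k−1}(b_k − 1).
- k = 3, p = 0.15: 0.15³ = 0.0034.
- k = 4: 0.15 × (3 × 0.15² × 0.85) = 0.0086, cumulative 0.0120.
- Through k = 24: **0.0468**, which agrees with at most 0.05.
- The same recursion gives 0.508 at rate 0.30 and 0.843 at rate 0.40.

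Figure 9 is sound. The issue is how it is applied.

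**Step 2. Compare two ways of applying it when DLTs are delayed.**
- As written, read literally: all DLTs seen so far against b_n, with n = patients who have started IL-2.
- Entry order: DLTs seen so far among the first k patients against b_k, for every k up to n.

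| DLT rate | Onset W | Ever flagged: as written / entry order | Flagged before 24th patient starts IL-2: as written / entry order |
|---|---|---|---|
| 0.30 | 27 weeks | about 0.45 / 0.51 | about 0.28 / 0.40 |
| 0.30 | 13 weeks | about 0.475 / 0.51 | – |
| 0.30 | 9 weeks | about 0.485 / 0.51 | about 0.41 / 0.445 |
| 0.30 | 4 weeks | about 0.50 / 0.51 | – |
| 0.40 | 27 weeks | about 0.82 / 0.84 | about 0.62 / 0.72 |

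With W = 27 weeks, the mean number of patients who have started IL-2 by the flag (24 if there is none) is 21.6 as written against about 20 in entry order at rate 0.30, and 18.3 against 16.3 at rate 0.40.

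At rate 0.15 the literal rule flags in about 0.025 to 0.04 of trials, depending on W, against 0.047 in entry order.

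Slower accrual shrinks the gap. With one patient per 1.5 months, onset over 6 months and rate 0.30, the chance of a flag before the 24th patient is 0.375 against 0.438.

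**Step 3. Why entry order keeps the 0.05.** At any time, the DLTs observed among the first k patients cannot exceed their final count. A flag at k therefore implies a crossing in the complete data, and every such crossing is seen once the DLTs have appeared. The final crossing probability through 24 patients is the value from Step 1, whatever the onset times.

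**The case against.** **The text does not say that only the current n is compared.** Section 8.5 summarises a published continuous-monitoring method and leaves the timing of checks open; a careful statistician could already apply it in entry order. That is fair. A reader might infer that the plan forbids looking back at earlier k, and it does not. But the words as printed compare DLTs with b_n out of n, with n fixed by the first IL-2 dose, and a team following them literally would under-flag.

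**Table 6a is a recording and reporting period.** It is tempting to call it the DLT window. Section 8.5 imports the event list without stating a window, and section 7.3 ends recording at a different point. What stands is that no window is given and both periods are long.

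**The size rests on assumptions.** This is correct. No document supports a uniform onset over 27 weeks or a DLT rate of 0.30 or 0.40. With onset over 13 weeks or less, the loss in ever flagging at rate 0.30 is about 1 to 3 points.

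**Few patients are spared.** Suspending accrual acts about 10 weeks before first IL-2, and patients already in B1 are not stopped by the rule. With that lead, at rate 0.30, the mean number reaching IL-2 is 22.3 against 21.1 (27-week onset) or 21.0 against 20.3 (13 weeks): about one patient.

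**There is other oversight.** Section 5.10 lists adverse reactions as a ground for termination, and section 10.6 lets the PI stop accrual and the PMC suspend or close the study. So this is not the only safety stop. Those routes are discretionary, and Figure 9 is the only one with a number attached.

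**Conclusion.** The point holds as a weakness in how the boundary is applied. Read literally, section 8.5 lets patients without follow-up raise the threshold, so a crossing among earlier patients can be flagged late or missed. The effect is mainly delay, of about one to two patients. At an assumed DLT rate of 0.30, the loss in ever flagging is about 6 points with 27-week onset and 2 to 3 points with 9-week onset. The loss in flagging before the 24th patient is about 12 points and 3 to 4 points. It is negligible if DLTs arise within about a month of first IL-2. These figures rest on the planned accrual and on assumed onset shapes and DLT rates.

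A reader might infer that the stated 0.05 is broken. It is not: delay pushes crossing at rate 0.15 below 0.047. Nor does the plan claim any power for this boundary that could fail. That the text sets no follow-up condition is certain; the size of the effect is not. The change is worth making because it is cheap.

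**What to change.** In section 8.5, add a rule of this form: order patients by first IL-2 dose; at each new DLT, compare the DLTs observed so far among the first k patients with b_k for every k from 3 to the current n, up to 24; suspend accrual if any k meets its boundary. Checking at each new DLT is enough, because b_k never falls and so a new patient alone cannot create a crossing.

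Three clarifications belong with it:
- Figure 9 ends at 24, while section 8.4 allows up to 26 patients with IL-2. State how patients 25 and 26 are handled; the 0.047 covers 24 only.
- Reconcile the ends of adverse event collection in section 7.3 and Table 6a for the DLT count, and state the window. Its length is for the sponsor to decide.
- Use one symbol for the number of patients; section 8.5 and Figure 9 mix n and k, and k is also used for the patients with DLTs.

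A shortcut to avoid is setting n to the patients who have either had a DLT or completed the window. DLTs then enter faster than non-events, and in simulation crossing at rate 0.15 rises to 0.086 with onset over 6 months and 0.125 over 9 months.

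The cost is a few sentences, with the same boundary, data and sample size. Suspensions at the acceptable rate become slightly more frequent, 0.047 against about 0.025 to 0.04, still within the stated 0.05.
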